The study sample size estimate is based on the evaluation of the primary immunogenicity objective of the study to demonstrate that the immune responses induced by 2 doses of C difficile vaccine (administered in a 0- and 6-month regimen) are noninferior to the immune responses induced by 3 doses of C difficile vaccine (administered in a 0-, 1-, and 6-month regimen) —by evaluating the toxin A– and toxin B–specific neutralizing antibody in terms of GMC ratios and the difference in percentage of participants achieving seroresponse, 1 month after the last investigational product administration. Seven hundred and eighty-four (784) evaluable participants per group will provide an overall power of 90.5% to meet the primary objective of noninferiority of a 2-dose to a 3-dose regimen for both toxin A and toxin B. 1 month after the last dose. The primary immunogenicity objective of noninferiority of the 2-dose regimen compared with the 3-dose regimen will be achieved if (1) the lower limit of the 2-sided 95% confidence interval (CI) for the GMC ratio (2-dose/3-dose regimen) is >0.67 for both toxin A and toxin B, and (2) the lower limit of the 2-sided 95% CI for the difference in percentage of participants achieving seroresponse (2-dose minus 3-dose regimen) is > -10% for both toxin A and toxin B 1 month after the last vaccination. The same criteria will be used for the secondary immunogenicity objective evaluation, which will be conducted only after the primary immunogenicity objective is met.

Assuming a maximum study nonevaluable rate of 20% and a randomization ratio of 1:1, a total of 1960 participants need to be randomized in the study to meet the primary immunogenicity objectives.

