For each of toxin A– and toxin B–specific neutralizing antibody levels, the GMC ratio of the 2-dose regimen to the 3-dose regimen at Month 7 and Month 12 will be evaluated by an analysis of covariance (adjusted for baseline antibody concentrations) and the corresponding 95% CIs. Two (2)-sided 95% CIs will be constructed by obtaining a CI for the mean of the logarithmically transformed assay results based on the Student t distribution, and transforming the confidence limits back to the original units. For each of the toxin A– and toxin B–specific neutralizing antibody levels, the difference between the 2-dose and 3-dose regimens in the percentage of participants achieving seroresponse at Month 7 and Month 12 will be computed, along with 95% CIs, using the Miettinen and Nurminen method. Seroresponse will be considered achieved if a participant has at least a 4-fold rise from baseline in the respective antibody concentration following vaccination. Baseline concentration is defined as the antibody concentration results from the blood drawn before vaccine Dose 1. Antibody concentration values below the LLOQ or denoted as below the limit of quantitation (BLQ) will be set to 0.5 × LLOQ for analysis.

All safety and reactogenicity endpoints will be summarized as proportions of participants with events by vaccine group. Additionally, exact 2-sided 95% CIs for proportions will be calculated using the Clopper-Pearson method.

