9.2. Sample Size Determination

In order to meet the immunogenicity primary objective, the study sample size estimate is based upon the evaluation of the primary immunogenicity objective of the study to demonstrate that the immune responses induced by 2 doses of C difficile vaccine (administered in a 0- and 6-month regimen) are noninferior to the immune responses induced by 3 doses of C difficile vaccine (administered in a 0-, 1-, and 6-month regimen) – by evaluating the toxin A- and toxin B- specific neutralizing antibody in terms of GMC ratios and difference in the percentage of participants achieving seroresponse, 1 month after the last investigational product administration. Regimen comparisons will be based on two primary endpoints: (1) the adjusted GMC ratio (adjusted for baseline antibody concentration); and (2) the difference in the percentage of participants achieving seroresponse, 1 month after the last vaccination (Month 7), and the corresponding 95% CIs. The noninferiority of a 2-dose regimen to a 3-dose regimen at 1 month after the last vaccine dose will be evaluated using a 1.5-fold NI margin for the adjusted GMC ratio and a 10% NI margin for the difference in seroresponse rates. Pfizer has developed a new assay which will be used for serology testing in this study. The new assay was used to test Study B5091009 retrospectively, and the standard deviation was evaluated. Therefore, the computation of the sample size for the GMC ratio is based on (1) the standard deviations (0.794 for toxin A and 1.059 for toxin B) from Study B5091009 data tested by the new assay and (2) an assumption that the true mean difference between the 2 regimens for both toxin A- and toxin B-specific neutralizing antibody levels is no more than 0.2 on the logarithmic scale. Similarly, the reference for the computation of the sample size for the difference in seroresponse rate is based on the percentage of seroresponse (4-fold rise from baseline) observed from Study B5091009, and an assumption that the true seroresponse rate for the 2-dose regimen is no more than 7% lower than the ones from the 3-dose regimen. A sample size of 784 evaluable participants per regimen will provide a power of 96.91% to declare the noninferiority of a 2-dose regimen to a 3-dose regimen for both toxin A and toxin B in terms of the GMC ratio, 1 month after the last dose (see Table 6). The sample size will also provide a power of 93.43% to declare the noninferiority of a 2-dose regimen to a 3-dose regimen for both toxin A and toxin B in terms of the difference of percentage of participants achieving seroresponse, 1 month after the last dose (see Table 7). Thus, the overall power to meet the study primary immunogenicity objective is 90.5%.

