
Table 6. Power Analysis (Primary Immunogenicity Objective: Noninferiority for GMC ratio)

Criteria	Neutralizing Antibody	Standard Deviation (Log Value) ^a	Assume Observed Log GMC Difference	Number of Evaluable Participants per Regimen	Power ^b	Power to Meet NI for Both Toxins at 1 Month After Dose 3
Lower limit of	Toxin A	0.794	0.2	784	99.92%	96.91%
95% CI for GMC ratio (2 doses/3 doses) > 0.67	Toxin B	1.059	0.2	784	96.99%	

Abbreviations: GMC = geometric mean concentration; NI = noninferiority.

Table 7. Power Analysis (Primary Immunogenicity Objective: Noninferiority for Difference in Seroresponse)

Criteria	Neutralizing Antibody	Observed % of seroresponse from 3-dose group ^a	Assume % of seroresponse from 2-dose group	Number of Evaluable Participants per Regimen	Power ^b	Power to Meet NI for Both Toxins at 1 Month After Dose 3
Lower limit of 95% CI for difference in seroresponse rate (2 doses minus 3 doses) > -10%	Toxin A	91.8%	86%	784	96.14%	93.43%
	Toxin B	93.7%	86%	784	97.18%	

Note: Seroresponse = Participant achieves at least a 4-fold rise after the last vaccination

If the primary immunogenicity objective is met, the secondary immunogenicity objective will be evaluated by the same criteria. For the secondary immunogenicity objective, if the noninferiority criterion for the GMC ratio is met at Month 12, then the evaluation of the difference between regimens in seroresponse at Month 12 will follow.

A sufficient number of participants will be screened to achieve 1960 participants randomly assigned to investigational product and 1568 evaluable participants (assuming a maximum study nonevaluable rate of 20% and a randomization ratio of 1:1), for an estimated total of 784 evaluable participants per vaccine group in order to meet the primary immunogenicity objectives.

a. Reference Study B5091009 tested by new assay, 1 month after Dose 3.

b. At 0.05 alpha level (2-sided).

a. Reference Study B5091009.

b. At 0.05 alpha level (2-sided).

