9.4.1. Immunogenicity Analyses

Endpoint	Statistical Analysis Methods
Primary	Adjusted GMC ratio of the 2-dose regimen to the 3-dose regimen for each of C difficile toxin A– and toxin B–specific neutralizing antibody levels at Month 7 will be computed using an analysis of covariance (adjusted for baseline antibody concentration); corresponding 95% CIs will be provided. The GMC will be calculated as the mean of the assay results after making the logarithm transformation and then transforming the value back to its original scale. Two (2) sided 95% CIs will be obtained by constructing a CI for the mean of the logarithmically transformed assay results based on the Student t distribution, and transforming the confidence limits back to the original units.
Secondary	The difference between the 2-dose regimen and the 3-dose regimen in the percentage of participants achieving seroresponse will be computed, along with 95% CIs, for each of the C difficile toxin A− and toxin B−specific neutralizing antibody levels at Month 7. For each of the toxin A− and toxin B-specific neutralizing antibody levels, for both seronegative (baseline concentration < LLOQ) and seropositive (baseline concentration ≥ LLOQ) participants, seroresponse is defined as at least a 4-fold rise from the baseline neutralizing antibody following vaccination. Two (2) sided 95% CIs will be constructed by the Miettinen and Nurminen method. Baseline concentration is defined as the antibody concentration results from the blood drawn before vaccine Dose 1. Antibody concentration values below the LLOQ or denoted as BLQ will be set to 0.5 × LLOQ for analysis. This analysis is based on the evaluable population in order to provide a comparison of the 2 regimens that has the greatest chance of identifying a difference between the regimens with respect to immunogenicity, if a meaningful difference actually exists (ie, results of the regimen comparisons fail to establish noninferiority). A secondary analysis will be performed based on the mITT population. Participants will be summarized according to the vaccine group to which they were randomized. Missing serology data will not be imputed. The secondary immunogenicity objective will be evaluated only after the primary immunogenicity objective is met.

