1. VERSION HISTORY

The statistical analysis plan (SAP) Version 1 for Study B5091019 is based on the protocol dated 02 May 2019. This SAP amendment (Version 2) is updated to align with some changes to the analysis as mentioned in Table 1.

Table 1. Summary of Major Changes in SAP Amendments

SAP Version	Change	Rationale			
1	Not applicable	Not applicable			
2	Minor updates in Section 2.2.2, Section 3.4.3, Section 3.5.2.1, Section 4.1, Section 4.2, Section 4.3, Section 5, Section 6 and Section 7.2.	 Following regulatory consultation, antibody concentration levels below the lower limit of quantitation (LLOQ) are imputed to the appropriate LLOQ value when determining seroresponse. Clarification was added to the duration calculations for reactogenicity events, based on Food and Drug Administration (FDA) comments for the study data standardization plan. Clarifications were added regarding the evaluable immunogenicity populations determined at Month 7 and Month 12. Immunogenicity analysis using the modified intent-to-treat (mITT) population will be limited based on the relative size of the mITT population. Clarification was added to identify participants to be included in specific vaccine regimens within the safety analysis population. Clarification was added to identify individual participant data cutoff time points for inclusion in the interim analyses. 			

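### Protocol Table 7's printed inputs give about 24% joint seroresponse power and 23% overall, not the stated 93.43% and 90.5%; the SAP's figures reproduce, but from a 3-point deficit and a different below-LLOQ rule

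*Protocol*

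**What the plan says.** Protocol 9.2 bases the seroresponse part of the sample size on Study B5091009 rates and on "an assumption that the true seroresponse rate for the 2-dose regimen is no more than 7% lower than the ones from the 3-dose regimen". Table 7 then lists, at 784 evaluable participants per regimen:

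- toxin A: 91.8% (3-dose), 86% (2-dose), power 96.14%;
- toxin B: 93.7% (3-dose), 86% (2-dose), power 97.18%;
- both toxins: 93.43%.

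The text repeats the joint figure ("The sample size will also provide a power of 93.43% to declare the noninferiority of a 2-dose regimen to a 3-dose regimen") and combines it with the 96.91% GMC power to reach 90.5% overall. The synopsis carries this forward: 784 "evaluable participants per group will provide an overall power of 90.5% to meet the primary objective of noninferiority".

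SAP 2.2.2 and Table 4 keep 784 per regimen but use 82.3% against 79.3% (toxin A) and 92.4% against 89.4% (toxin B), a 3-point deficit. The stated powers are 93.93%, 99.7%, 93.64% jointly and 90.7% overall.

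The two documents also derive seroresponse differently. The protocol's seroresponse paragraph in 9.4.1 says "Antibody concentration values below the LLOQ or denoted as BLQ will be set to 0.5 × LLOQ for analysis", as does the synopsis, and the Table 7 note gives no below-LLOQ rule. SAP Table 1 reports that, after regulatory consultation, concentrations below the LLOQ "are imputed to the appropriate LLOQ value when determining seroresponse". SAP 3.4.3, SAP 5 and the Table 4 note apply that rule and keep 0.5 × LLOQ for GMC.

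**The concern.** Table 7 looks wrong before any calculation. Toxin B has the same 2-dose rate, sample size and margin as toxin A and a larger deficit (93.7 − 86 = 7.7 points, against 91.8 − 86 = 5.8), yet the higher stated power. The toxin B deficit also breaks the limit of 7% in the text, read either as points (7.7) or as a relative reduction (7.7/93.7 = 8.2%).

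The figure at stake is the stated power of the primary objective. A reader of the protocol or synopsis learns that the trial has about 90% power even if the 2-dose seroresponse rate is up to 7% lower. With a 10-point margin, a true 7-point deficit leaves only 3 points of room. Two current documents also justify the same sample size with different deficits and different derivations of a coprimary endpoint.

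**Working it through.** **Inputs.** n = 784 per arm; seroresponse margin 10 points; lower limit of a 2-sided 95% Miettinen-Nurminen interval (Protocol 9.2 and 9.4.1); rates from Protocol Table 7 and SAP Table 4; GMC standard deviations 0.794 and 1.059, true log difference 0.2, margin ln 1.5 = 0.4055.

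**Figures that reproduce.** GMC power = Φ[(0.4055 − 0.2)/SE − 1.96], with SE = SD × √(2/784).

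- Toxin A: SE = 0.0401; 5.123 − 1.960 = 3.163; 99.92% (stated 99.92%).
- Toxin B: SE = 0.0535; 3.841 − 1.960 = 1.881; 97.0% (stated 96.99%).

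The protocol multiplies, that is, it treats the toxins and the two criteria as independent: 0.9614 × 0.9718 = 0.9343, and 0.9343 × 0.9691 = 0.905. These products are consistent, so the fault lies in the per-toxin seroresponse powers or in the rates printed beside them.

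**Table 7 by hand.** Power ≈ Φ[(0.10 − (p₃ − p₂))/SE − 1.96], with SE = √{[p₃(1 − p₃) + p₂(1 − p₂)]/784}.

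- Toxin A: SE = √[(0.0753 + 0.1204)/784] = 0.01580; 0.042/0.01580 = 2.659; Φ(0.699) = 75.8%.
- Toxin B: SE = √[(0.0590 + 0.1204)/784] = 0.01513; 0.023/0.01513 = 1.520; Φ(−0.440) = 33.0%.

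**Exact calculation.** Both binomials were enumerated (784 each), and noninferiority was declared when the Miettinen-Nurminen score statistic at −0.10 exceeded 1.96. Overall power is the joint power × 0.9691.

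| Inputs | Toxin A | Toxin B | Joint | Overall |
|---|---|---|---|---|
| Protocol Table 7, stated | 96.14% | 97.18% | 93.43% | 90.5% |
| Protocol Table 7, recomputed | 74.6% | 32.0% | 23.9% | 23.1% |
| Protocol 3-dose rates, 7 points lower | 45.1% | 50.6% | 22.8% | 22.1% |
| Protocol 3-dose rates, 7% relative | 59.8% | 62.7% | 37.5% | 36.3% |
| SAP Table 4, stated | 93.93% | 99.7% | 93.64% | 90.7% |
| SAP Table 4, recomputed | 94.0% | 99.7% | 93.8% | 90.9% |

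**Other methods.** Pooled, unpooled, restricted-variance (Farrington-Manning) and continuity-corrected calculations put toxin A at 73% to 76% and toxin B at 30% to 33%. A one-sided 0.05 test would give only 83.7% and 44.1% (exact).

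**Correlation.** Joint power cannot exceed the smaller single power, 32.0%, and cannot fall below 0.746 + 0.320 − 1 = 6.6%.

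**What the stated powers would need.** With the printed 3-dose rates, the 2-dose rates would have to be about 87.6% (A) and 89.3% (B), deficits of about 4.2 and 4.4 points.

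**Sensitivity at the SAP's 3-dose rates.** Joint seroresponse power is 93.8% at a 3-point deficit, 82.9% at 4, 62.5% at 5 and 14.3% at 7.

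**Below-LLOQ rule.** For a participant below the LLOQ at baseline, a 4-fold rise means reaching 4 × 0.5 × LLOQ = 2 × LLOQ under the protocol, but 4 × LLOQ under the SAP. The SAP rule is stricter for these participants, which fits its lower reference rates.

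**The case against.** The strongest reply is that the 86% in Table 7 may be the misprint and the powers correct. It is the only rate there without a decimal, and it appears in both rows. That cannot be excluded, so 23% is what the printed assumptions imply and not a forecast for the trial. It does not rescue the protocol, though: the text's own limit of 7% gives only 45.1% and 50.6% in points, or 59.8% and 62.7% in relative terms.

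Second, the product rule is doubtful, because GMC and seroresponse come from the same assay results. This is fair, and the 32.0% ceiling is the figure that does not depend on it.

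Third, SAP Version 2 lists Section 2.2.2 among its updated sections and already holds a calculation that reproduces, and both documents allow the SAP to modify the protocol's plans. This limits the harm, but the protocol and synopsis still state the old figures.

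Fourth, adopting the SAP's 3-point deficit makes the documents agree without showing that 3 points is a sound assumption. This stands, and is why the reason for it has to be recorded. The below-LLOQ change does not supply that reason. Nor can it be shown to account fully for the changed reference rates, since toxin A falls by 9.5 points (91.8 to 82.3) and toxin B by 1.3 (93.7 to 92.4).

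**Conclusion.** The concern holds. Table 7's printed rates and printed powers are incompatible: 74.6% and 32.0% against 96.14% and 97.18%. Joint seroresponse power is 23.9% and overall power 23.1% if the protocol's multiplication is kept, against 93.43% and 90.5%; under any correlation, joint power is at most 32.0%. These figures rest on 784 evaluable per arm, the 10-point margin, the 2-sided 95% Miettinen-Nurminen limit and the rates as printed. Which entry is wrong cannot be settled from the documents.

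The SAP's calculation is sound for its own inputs, so about 90% overall power is supported for a true deficit of about 3 points at its reference rates, and not for 7%. The fault is a misstated planned power, an unexplained change of deficit, and two below-LLOQ rules for one coprimary endpoint. It does not touch the test, the margin or the success criteria, and should be fixed rather than treated as fatal.

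**What to change.** Keep the sample size, margin and decision rule.

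1. In Protocol 9.2, Table 7 and the synopsis, withdraw 96.14%, 97.18%, 93.43%, 90.5% and the limit of 7% wherever they appear. Replace them with the SAP Table 4 inputs and powers: 82.3%/79.3% and 92.4%/89.4%; 93.93%, 99.7% and 93.64%; overall 90.7%.
2. In the same amendment, carry the SAP's below-LLOQ rule into the synopsis, both seroresponse paragraphs of 9.4.1 (Month 7 and Month 12) and the Table 7 note: the LLOQ for seroresponse, 0.5 × LLOQ for GMC.
3. State that about 90% overall power holds for a true deficit of about 3 points at these rates, and that joint seroresponse power is 62.5% at 5 points and 14.3% at 7.
4. Record in SAP Table 1 why the deficit was changed from 7% to 3%. If the sponsor still regards 7% as plausible, it should say so beside these figures.

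The cost is one protocol amendment, which needs IRB/EC approval under Protocol 10.1.1, and one line in SAP Table 1. There are no extra participants and no change to the test. The stated power becomes visibly less favourable for deficits above 3 points.

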9.3. Populations for Analysis

For purposes of analysis, the following populations are defined:

[figure not shown]
Population	Description
Enrolled	All participants who sign the ICD.
Randomly assigned to investigational product	All participants who are assigned a randomization number in the IWR system.
Evaluable	All participants who are eligible, have received the investigational product to which they were randomized, have blood drawn for assay testing within the specified time frame, have valid and determinate assay results for either toxin A or toxin B for the proposed analysis time point, and have no major protocol violations.
	For participants who have major protocol violations (eg, took concomitant medications/vaccines that may impact the immune response), all postviolation observations will be censored.
	Participants who discontinue the study before reaching primary endpoint will be excluded from the primary analysis.
Modified intent-to-treat (mITT)	All participants who are randomly assigned to investigational product and have received at least 1 vaccination and have at least 1 valid and determinate assay result for the proposed analysis.
	Participants who discontinue the study before reaching the primary endpoint will be excluded from the analysis.
Safety	All participants who are randomly assigned to investigational product and have received at least 1 dose of investigational product.
	For reactogenicity, it includes all participants who receive the dose and have the e-diary collected; an indicator variable for an e-diary completion status after each dose will be detailed in the SAP.
	For safety, it includes all participants who receive at least 1 dose. Standard algorithms for handling missing AE dates and missing AE severity will be applied following the Safety Rulebook Summary developed by Pfizer.

9.4. Statistical Analyses

The SAP will be developed and finalized before database lock and will describe the participant populations to be included in the analyses, and procedures for accounting for missing, unused, and spurious data. This section provides a summary of the planned statistical analyses of the primary and secondary endpoints.

9.4.1. Immunogenicity Analyses

Endpoint	Statistical Analysis Methods
Primary	Adjusted GMC ratio of the 2-dose regimen to the 3-dose regimen for each of C difficile toxin A– and toxin B–specific neutralizing antibody levels at Month 7 will be computed using an analysis of covariance (adjusted for baseline antibody concentration); corresponding 95% CIs will be provided. The GMC will be calculated as the mean of the assay results after making the logarithm transformation and then transforming the value back to its original scale. Two (2) sided 95% CIs will be obtained by constructing a CI for the mean of the logarithmically transformed assay results based on the Student t distribution, and transforming the confidence limits back to the original units.
Secondary	The difference between the 2-dose regimen and the 3-dose regimen in the percentage of participants achieving seroresponse will be computed, along with 95% CIs, for each of the C difficile toxin A− and toxin B−specific neutralizing antibody levels at Month 7. For each of the toxin A− and toxin B-specific neutralizing antibody levels, for both seronegative (baseline concentration < LLOQ) and seropositive (baseline concentration ≥ LLOQ) participants, seroresponse is defined as at least a 4-fold rise from the baseline neutralizing antibody following vaccination. Two (2) sided 95% CIs will be constructed by the Miettinen and Nurminen method. Baseline concentration is defined as the antibody concentration results from the blood drawn before vaccine Dose 1. Antibody concentration values below the LLOQ or denoted as BLQ will be set to 0.5 × LLOQ for analysis. This analysis is based on the evaluable population in order to provide a comparison of the 2 regimens that has the greatest chance of identifying a difference between the regimens with respect to immunogenicity, if a meaningful difference actually exists (ie, results of the regimen comparisons fail to establish noninferiority). A secondary analysis will be performed based on the mITT population. Participants will be summarized according to the vaccine group to which they were randomized. Missing serology data will not be imputed. The secondary immunogenicity objective will be evaluated only after the primary immunogenicity objective is met.
	Adjusted GMC ratio of the 2-dose regimen to the 3-dose regimen for each of C difficile toxin A– and toxin B–specific neutralizing antibody levels at Month 12 will be computed using an analysis of covariance (adjusted for baseline antibody concentration); corresponding 95% CIs will be provided. The GMC will be calculated as the mean of the assay results after making the logarithm transformation and then transforming the value back to its original scale. Two (2) sided 95% CIs will be obtained by constructing a CI for the mean of the logarithmically transformed assay results based on the Student t distribution, and transforming the confidence limits back to the original units.
	The difference between the 2-dose regimen and the 3-dose regimen in the percentage of participants achieving seroresponse will be computed, along with 95% CIs, for each of C difficile toxin A– and toxin B–specific neutralizing antibody levels at Month 12. For each of toxin A- and toxin B-specific neutralizing antibody levels, for both seronegative (baseline concentration $<$ LLOQ) and seropositive (baseline concentration \ge LLOQ) participants, seroresponse is defined as at least a 4-fold rise from the baseline neutralizing antibody following vaccination. Two (2) sided 95% CIs will be constructed by the Miettinen and Nurminen method. Antibody concentration values below the LLOQ or denoted as BLQ will be set to $0.5 \times$ LLOQ for analysis.
	This analysis is based on the evaluable population in order to provide a comparison of the 2 regimens that has the greatest chance of identifying a difference between the regimens with respect to immunogenicity, if a meaningful difference actually exists (ie, results of the regimen comparisons fail to establish noninferiority). A secondary analysis will be performed based on the mITT population. Participants will be summarized according to the vaccine group to which they were randomized. Missing serology data will not be imputed.

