Criteria	Neutralizing Antibody	Standard Deviation (Log Value) ^a	Assumed Observed Log GMC Difference	Number of Evaluable Participants per Regimen	Power ^b	Power to Meet NI for Both Toxins at 1 Month After Dose 3
Lower limit of 95% CI for GMC ratio	Toxin A	0.794	0.2	784	99.92%	96.91%
(2 doses/3 doses) >0.67	Toxin B	1.059	0.2	784	96.99%	

Abbreviations: GMC = geometric mean concentration; NI = noninferiority

- a. Reference Study B5091009 tested by the new assay, 1 month after Dose 3.
- b. At 0.05 alpha level (2-sided).

Table 4. Power Analysis (Primary Immunogenicity Objective: Noninferiority for Difference in Seroresponse)

Criteria	Neutralizing Antibody	_	Assumed % of Seroresponse From 2-Dose Group	-	Power ^b	Power to Meet NI for Both Toxins at 1 Month After Dose 3
Lower limit of 95% CI for difference of	Toxin A	82.3%	79.3%	784	93.93%	93.64%
seroresponse rate (2 doses minus 3 doses) > -10%	Toxin B	92.4%	89.4%	784	99.7%	

Abbreviations: BLQ = below the limit of quantitation; LLOQ = lower limit of quantitation; NI = noninferiority.

Note: Seroresponse = participant achieves at least a 4-fold rise after the last vaccination (antibody concentration levels below the LLOQ or denoted as BLQ will be set to the appropriate LLOQ value).

- a. Reference Study B5091009.
- b. At 0.05 alpha level (2-sided).

A sufficient number of participants will be screened to achieve 1960 participants randomly assigned to investigational product and 1568 evaluable participants (assuming a maximum study nonevaluable rate of 20%), for an estimated total of 784 evaluable participants per vaccine group in order to meet the primary immunogenicity objectives.

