3.4.3. Baseline Serostatus

Individual participants' baseline serostatus (prior to the first vaccination) will be defined based on the LLOQ values for *C difficile* toxin A– and toxin B– specific neutralizing antibody levels as outlined below.

- Toxin A+: baseline toxin A–specific neutralizing antibody level ≥ LLOQ for toxin A-specific neutralizing antibody level
- Toxin A—: baseline toxin A—specific neutralizing antibody level < LLOQ for toxin A-specific neutralizing antibody level
- Toxin B+: baseline toxin B–specific neutralizing antibody level ≥ LLOQ for toxin B-specific neutralizing antibody level
- Toxin B—: baseline toxin B—specific neutralizing antibody level <LLOQ for toxin B-specific neutralizing antibody level

In addition, the following 4 groups will also be defined.

- Toxin A+/toxin B+: baseline serostatus is both toxin A+ and toxin B+
- Toxin A+/toxin B-: baseline serostatus is toxin A+ and toxin B-
- Toxin A-/toxin B+: baseline serostatus is toxin A- and toxin B+
- Toxin A-/toxin B-: baseline serostatus is both toxin A- and toxin B-

CCI

For the assessments of

seroresponse difference at Month 7, at Month 12, and at Month 7 and Month 12 by age group, as well as the summary of fold rise, the *C difficile* toxin A– or toxin B–specific neutralizing antibody concentration levels below the LLOQ or denoted as below the limit of quantitation (BLQ) will be set to the appropriate LLOQ value.

For GMC and GMFR analysis, the antibody levels that are below the LLOQ or denoted as BLQ will be assigned a value of $0.5 \times LLOQ$.

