5. GENERAL METHODOLOGY AND CONVENTIONS

The immunogenicity data will be summarized according to the vaccine regimen as received for participants in the EI7 (or EI12 as appropriate) population and according to the vaccine regimen as randomized in the mITT population.

For the assessments of seroresponse difference at Month 7, Month 12, and at Month 7 and Month 12 by age group, as well as the summary of fold rise, the *C difficile* toxin A– or toxin B–specific neutralizing antibody concentration levels below the LLOQ or denoted as BLQ will be set to the appropriate LLOQ value.

For GMC and GMFR analysis, the antibody levels that are below LLOQ or denoted as BLQ will be assigned a value of $0.5 \times \text{LLOQ}$. Missing serology data will not be imputed.

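### Protocol and SAP substitute different values below LLOQ for the co-primary seroresponse endpoint, and the protocol's seroresponse power figures do not follow from its own rates

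*Protocol*

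**What the plan says.** Protocol section 9.4.1 gives the rule inside the seroresponse text, for Month 7 and again for Month 12: "Antibody concentration values below the LLOQ or denoted as BLQ will be set to 0.5 × LLOQ for analysis". The synopsis places the same rule directly after its seroresponse definition: values below LLOQ "will be set to 0.5 × LLOQ for analysis". Neither place makes an exception for seroresponse.

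SAP version 2, section 5, says that for the seroresponse difference and the fold-rise summary the "neutralizing antibody concentration levels below the LLOQ or denoted as BLQ will be set to the appropriate LLOQ value". The note to SAP Table 4 repeats this. SAP section 3.4.3 keeps the half-LLOQ value for the other analyses only: "For GMC and GMFR analysis, the antibody levels that are below the LLOQ or denoted as BLQ will be assigned a value of" 0.5 × LLOQ. The version history gives the reason: "Following regulatory consultation, antibody concentration levels below the lower limit of quantitation (LLOQ) are imputed to the appropriate LLOQ value when determining seroresponse". It lists the change among minor updates.

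Both documents define seroresponse as at least a 4-fold rise from baseline, whatever the baseline serostatus. Both let the SAP modify the protocol, and both say that major changes to the primary endpoint definition or its analysis will also appear in a protocol amendment (protocol section 9; SAP section 2).

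The planning assumptions differ too. Protocol section 9.2 takes the true 2-dose rate to be "no more than 7% lower than the ones from the 3-dose regimen". SAP section 2.2.2 takes 3%. The tables are:

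| Table | Toxin | 3-dose | 2-dose | Printed power | Both toxins |
|---|---|---|---|---|---|
| Protocol Table 7 | A | 91.8% | 86% | 96.14% | 93.43% |
| | B | 93.7% | 86% | 97.18% | |
| SAP Table 4 | A | 82.3% | 79.3% | 93.93% | 93.64% |
| | B | 92.4% | 89.4% | 99.7% | |

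**The concern.** Seroresponse noninferiority for both toxins is part of the primary success criterion. The two operative texts classify some of the same participants differently on that endpoint, so the protocol states a rule that will not be used for the primary decision.

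The protocol's planning figures raise a second, independent problem. They rest on different reference rates and a different assumed deficit from the SAP's. The toxin B row of Table 7 assumes a deficit of 93.7 − 86 = 7.7 points, which is larger than the stated maximum of 7. It nevertheless carries the higher printed power of the two toxins. If the printed powers are wrong, the protocol's record of why 784 evaluable participants per regimen is enough is wrong as well.

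**Working it through.** **Responder cut-off for a participant below LLOQ at baseline**

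- Protocol: 4 × 0.5 LLOQ = 2 × LLOQ.
- SAP: 4 × 1 LLOQ = 4 × LLOQ.

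A post-vaccination level from 2 to just under 4 × LLOQ is a response under the protocol and a non-response under the SAP. A participant at or above LLOQ at baseline needs at least 4 × LLOQ under either rule, so is unaffected. Moving from the protocol rule to the SAP rule can therefore only remove responders.

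**Power: inputs and formula**

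Both documents give n = 784 per arm, a margin of 10 points and a two-sided alpha of 0.05. With unpooled variance:

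power = Φ[(0.10 − (p3 − p2)) / SE − 1.96], where SE = √[(p3(1 − p3) + p2(1 − p2)) / 784].

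Each case was also checked with the restricted-MLE (Farrington-Manning) formula and by exact enumeration of the Miettinen-Nurminen test.

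*Protocol Table 7*

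- Toxin A: SE = √[(0.918 × 0.082 + 0.86 × 0.14) / 784] = 0.01580. (0.10 − 0.058) / 0.01580 − 1.96 = 0.70, so power is 75.8% (restricted MLE 74.4%, exact 74.6%). Printed: 96.14%.
- Toxin B: SE = √[(0.937 × 0.063 + 0.86 × 0.14) / 784] = 0.01513. (0.10 − 0.077) / 0.01513 − 1.96 = −0.44, so power is 33.0% (31.9%, 32.0%). Printed: 97.18%.
- Both toxins: joint power cannot exceed the smaller of the two, about 33%, whatever their correlation. The product that the document's approach uses is 0.758 × 0.330 = 25.0%. Printed: 93.43%.

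The multiplication steps in the protocol are right (0.9614 × 0.9718 = 0.9343; 0.9691 × 0.9343 = 0.905). The error is in the two toxin-specific powers, and 90.5% inherits it.

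Alternative readings (unpooled) do not recover the printed values:

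- One-sided alpha of 0.05: 84.5% and 45.0%.
- A flat 7-point deficit from the listed 3-dose rates: 46.0% and 52.1%.
- A flat 3-point deficit: 99.7% and 99.9%.

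The printed powers would need deficits of about 4.2–4.3 points (A) and 4.4–4.6 points (B).

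*SAP Table 4*

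- Toxin A (82.3 vs 79.3): SE = 0.01988. 0.07 / 0.01988 − 1.96 = 1.56, so power is 94.1% (93.9%, 94.0%). Printed: 93.93%.
- Toxin B (92.4 vs 89.4): SE = 0.01451. 0.07 / 0.01451 − 1.96 = 2.87, so power is 99.8% (99.7%, 99.7%). Printed: 99.7%.

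The same method reproduces the SAP, so the method does not explain the failure of Table 7.

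**How far the SAP figures depend on the 3-point deficit**

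SAP 3-dose rates, 784 per arm, unpooled / restricted MLE:

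| True deficit (points) | Toxin A power | Toxin B power |
|---|---|---|
| 3 | 94.1 / 93.9% | 99.8 / 99.7% |
| 4 | 84.9 / 84.7% | 98.1 / 97.7% |
| 5 | 69.5 / 69.3% | 90.9 / 89.8% |
| 6 | 50.0 / 49.9% | 73.4 / 71.9% |
| 7 | 30.8 / 30.8% | 47.7 / 46.5% |

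**Shift in the 3-dose reference rates**

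Toxin A: 91.8 − 82.3 = 9.5 points. Toxin B: 93.7 − 92.4 = 1.3 points. The direction fits a stricter cut-off, and the note to SAP Table 4 names the LLOQ rule, but neither document says that the rule accounts for the shift.

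**The case against.** The best reply is that the governing rule is already settled. The protocol lets the SAP modify it. SAP version 2 logs the change with its reason and applies it consistently. The 4-fold definition, margin, interval method and time point are the same in both documents. An amendment is promised only for major modifications, and the SAP classes this one as minor. The rule applies equally to both arms, and the documents do not give the share of participants between 2 and 4 × LLOQ, so no effect on the verdict is shown. The SAP has also restated the planning figures, and they support 784 per regimen. Finally, Table 7's arithmetic and the change of deficit are separate from the LLOQ rule, and neither document plans for a 7-point deficit at SAP rates.

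Much of this stands. An analyst following the SAP would apply the LLOQ value, and whether the change is major is a judgement, although it doubles the cut-off for every participant seronegative at baseline. The three matters are distinct and are kept apart here. The 7-point row is a stress case that joins one document's deficit to the other's rates. What the reply does not remove is that the protocol states a rule that will not be used for a co-primary endpoint, and prints powers that its own inputs contradict. The SAP's restated figures do not correct the protocol, and they give no reason for moving from 7 to 3 points.

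**Conclusion.** The concern holds and should be fixed. For participants below LLOQ at baseline the responder cut-off is 2 × LLOQ in the protocol and 4 × LLOQ in the SAP. This follows directly from the two texts and needs no further assumption. The effect on the between-arm difference, and so on the noninferiority conclusion, is unknown from the documents.

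Separately, the protocol's seroresponse power (93.43%) and overall power (90.5%) are wrong as written: on Table 7's own rates, power for both toxins is at most about 33%. This rests on 784 per arm, the 10-point margin and two-sided alpha of 0.05, and three calculation methods agree to within about 1.5 points. The sample size is supported by the SAP's figures, provided that the true deficit is about 3 points. At 5 points, toxin A power is already down to about 69%.

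**What to change.** 1. Amend the protocol synopsis and both seroresponse paragraphs of section 9.4.1 to the SAP rule: LLOQ for seroresponse, 0.5 × LLOQ for GMC and GMFR. State that this rule governs the primary decision.
2. Restate the protocol's seroresponse planning figures (synopsis, section 9.2, Table 7) on the reference rates for that rule, and say why those rates differ from the ones now printed. Do not carry forward 96.14%, 97.18%, 93.43% or 90.5%.
3. Treat the assumed true deficit as its own item. State it, justify it independently of the LLOQ rule, and show power from 3 to 7 points.
4. Optionally, report Month 7 and Month 12 seroresponse with 0.5 × LLOQ as a sensitivity analysis.

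The cost is a short amendment: one sentence in each of three places, the section 9.2 text, the synopsis power figure and Table 7. It also needs whatever IRB/EC approval protocol section 10.1.1 requires. No new data are needed. The sample size stays at 784 evaluable per regimen if the 3-point deficit can be justified; if 7 points is kept at the SAP rates, it would have to be revisited.
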